1. STUDY SYNOPSIS

Study Title	Postoperative Delirium: Brain Vulnerability and Recovery
Objectives	
 1. Characterize whether EEG slowing or DMN functional connectivity (FC) distinguishes epochs during delirium from those following resolution of symptoms. 2. Assess whether DMN FC after recovery from delirium is weaker than DMN FC in those who did not experience delirium. 3. Investigate the relationship between preoperative DMN FC and postoperative delirium.
Study Period	
Planned enrollment duration: 1-2 years
 
Planned study duration: 4-5 days per subject: (Preoperative testing) ~2 hours within one month before surgery; (Postoperative session 1-3) ~1 hour between post-operative days 1-8; (Postoperative session 4) ~2 hours during the period between disconnection of chest tubes and within 1 month after hospital discharge.

Study Design	Single academic center, prospective, observational, longitudinal, case-control trial
Number of Patients	
Target enrollment: 66 (evaluable) participants recruited from the Barnes-Jewish Hospital (BJH) Center for Preoperative Assessment and Planning (CPAP), BJH Center for Advanced Medicine (CAM), Cardiothoracic Intensive Care Unit (CT-ICU), or step-down floors.
 
Delirium Case Arm: 33 patients diagnosed with postoperative delirium after surgery
 
Postoperative Control Arm: 33 control patients without postoperative delirium after surgery

Inclusion and Exclusion Criteria	
Common Inclusion Criteria: Age \geq 60, surgery requiring cardiopulmonary bypass (CPB) for coronary artery bypass grafting, aortic repair/replacement, septal myectomy, and/or heart valve repair/replacement, English speaking
 
Common Exclusion Criteria: Implanted pacemaker, automatic internal cardiac defibrillator, or other implant for which non-contrast magnetic resonance imaging (MRI) is contraindicated; concomitant cerebrovascular procedure or requirement of deep hypothermic circulatory arrest; inability to lay flat or still for MRI; legal blindness or severe deafness; seizure history, known focal brain lesion larger than 3 cm
 
Delirium Case Arm: Delirious as diagnosed by the Confusion Assessment Method (CAM)/Confusion Assessment Method for the Intensive Care Unit (CAM-ICU) at some point during postoperative day 1-5.
 
Postoperative Control Arm: Not delirious as diagnosed by the CAM/CAM-ICU on postoperative day 1-5.

Measurements	
Primary:
 
(1) EEG before surgery, during delirium, and after recovery: Delta (0.5-4 Hz), theta (4-8 Hz), and alpha (8-13 Hz) EEG power from 1 minute of continuous artifact-free data acquired during 30 minutes of eyes open wakefulness and 15 minutes of eyes closed wakefulness within one month before surgery and after surgery between POD 1-8.
 
(2) FC Diffuse Optical Tomography (fcDOT) before surgery, during delirium, and after recovery: FC between anterior and posterior DMN regions assessed from a total of 30 minutes of fcDOT data with eyes open wakefulness, a total of 15 minutes of eyes closed wakefulness, and 3 minutes while listening to an audio recording within one month before surgery and after surgery between POD 1-8.
 
(3) Non-contrast fcMRI of patients before and after surgery in both individuals who do and do not develop delirium: FC between anterior and posterior DMN regions assessed from 20 minutes of resting-state fcMRI acquired with eyes open wakefulness within one month before surgery and after surgery during the period between disconnection of chest tubes and within 1 month after hospital discharge.
 
Secondary:
 
(1) fcDOT and EEG from patient controls
 
(2) Patient Demographics, including age and years of education, surgical and anesthetic exposure

Outcomes	
(1) Delirium incidence as assessed by the CAM/CAM-ICU.
 
(2) Delirium severity subscores as assessed by the CAM-S.
 
(3) Delirium duration as the number of days with CAM+ listed in patient records.
 
(4) Pain level using the BPS/BPS-NI and VAS Pain scores.

2. STUDY PROTOCOL

2.1 Background, Significance, and Preliminary Data

2.1.1 Postoperative Delirium

Postoperative delirium is a potentially life-threatening under-diagnosed disorder that costs the US billions of dollars annually[1]. An incidence of up to 50% follows both non-cardiac[2] and cardiac[3] procedures. Post-cardiac surgery delirium prolongs hospitalization[4], and is associated with greater risks of persistent functional decline [5-7] and mortality[4, 8]. Diagnosis and treatment are urgent to reduce self-injurious behavior and interference of rehabilitation but significant barriers exist. By definition, delirium manifests acutely with fluctuations of inattention and disordered cognition[9], so timing of assessment may preclude detection. Without direct verbal interrogation, clinicians can misdiagnose[10-12] the predominant hypoactive subtype[13], that manifests as disorganized thought and disengagement without agitation[14]. Lastly, manifestation peaks 1-2 days postoperatively[13, 15] but may vary in onset and reoccurrence. Neither pre- nor post-operative assays exist to predict incidence of this perioperative complication.

2.1.2 Encephalographic Markers of Postoperative Delirium

Electroencephalographic (EEG) changes have been noted during delirious episodes since 1944[16] but systematic longitudinal studies are lacking. Slowing in EEG[17], with patterns mirroring those observed during sleep and general anesthesia, are generally observed during hypoactive delirium, despite maintenance of arousal. Alpha and beta (12-20 Hz) rhythms are replaced by slower theta (4-8 Hz)[18-20] and delta (<4 Hz)[18, 19, 21]. A recent meta-analysis of postoperative delirium highlighted the lack of standard EEG markers used quantitatively by investigators[22]. Of the 14 investigations, some relied on reduction in relative alpha power[23-27], while others studied the increase in relative theta power[23, 24, 26-30] or increase in relative delta[20-22, 24, 26, 27, 29, 31]. A recent case-control study[31] revealed significant differences between delirious patients and their controls for these three metrics and for three others. These results were striking because significant differences between the two groups were observed across *all* electrode combinations studied (80 for eyes open and 210 for eyes closed). These widespread significant findings, high sensitivities (> 88%), and high specificities (>92%) require validation in longitudinal studies where patients serve as their own controls after delirium resolution. Controls to ensure that wakefulness has been maintained would aid in interpretation. Finally, such longitudinal studies would address whether aspects of EEG slowing (change in delta, theta, and/or alpha power) persist after recovery from acute manifestations of delirium. These aspects of validation would be needed to determine whether EEG may aid in routine surveillance for postoperative delirium.

2.1.3 Structural Neuroimaging of Delirium Vulnerability

Structural magnetic resonance imaging (MRI) has been investigated as a means identifying brain abnormalities posited to confer vulnerability for postoperative delirium[32]. Their existence has been suggested by preoperative risk factors of age[2], years of education, existing cognitive impairment[33], and even stroke without residual symptoms[34, 35]. Retrospective MRI of delirious patients implicated white matter disruption[36, 37], hyperintensities consistent with stroke [38], and total brain volume[39]. However, these markers demonstrated little prognostic value in recent prospective studies[32, 40]. As an alternative, characterizing the functional derangements within the brain prospectively may yield markers for vulnerability or insight into the etiology of delirium.

2.1.4 Functional Neuroimaging

In contrast to structural MRI, functional MRI has yielded insight into how distributed brain activity relates to cognition and behavior. This technique relies on relative changes in the blood-oxygen level dependent (BOLD) signal as a surrogate of altered blood flow reflecting underlying neural activity. Functional connectivity (FC) MRI

identifies brain regions with slow correlated fluctuations in the BOLD signals during passive wakefulness. These distributed brain regions with highly correlated signals recapitulate spatial patterns of BOLD activity observed during task paradigms. Functional connectivity (FC) describes the correlation strength between these components brain regions, which are collectively referred to as resting-state networks (RSNs).

2.1.5 The Default Mode Network

The Default Mode Network (DMN)[42] is an archetypal RSN[43] widely distributed across the cerebral cortex (**Figure 1**). The DMN contains regions that are most active during quiet resting[42] and are negatively correlated with those of other RSNs implicated in attention[44] and salience detection[45]. It plays a putative role in self-referential cognition and episodic memory[46]. Reduction of FC within the DMN occurs during slow-wave sleep[47, 48], coma[49], and anesthetic-induced unconsciousness[41, 50], and correlates with severity of Alzheimer's dementia[51, 52]. Moreover, alterations in DMN FC precede clinical dementia symptoms[53-55]. These observations are consistent with our hypothesis that latent DMN FC abnormalities in ostensibly normal patients reflect susceptibility to perioperative delirium. Our fcMRI study of healthy volunteers rendered unresponsive with sevoflurane demonstrated weakening of FC within the DMN (**Figure 2**)[41], suggesting that DMN FC is likely weakened during general anesthesia. Whether inflammation and surgical factors implicated in delirium pathogenesis converge on a vulnerable DMN remains unknown. Reduced DMN FC, as a marker of delirium, is supported by the weakening of DMN MRI FC between anterior and posterior regions during delirium compared to control patients (**Figure 3**)[56]. While suggestive, the role DMN FC as a MRI marker of delirium pathogenesis has not been established.

[figure not shown]

Figure 1. Superficial and deep regions of the Default Mode Network (DMN). Transverse and sagittal atlas sections with superimposed resting-state networks (RSNs) are shown. The DMN (red) contains deep regions (mPFC and PCC) and superficial cortical regions (MFG and IPL). Temporal regions are not shown. Other RSNs are shown in different colors. Adapted from [name] et al., 2015[41].

[figure not shown]

Figure 2. Reduction of DMN FC during sevoflurane sedation. **A.** PCC region. **B.** Transverse and sagittal sections showing PPC FC to the medial prefrontal cortex (mPFC) and superficial regions of the inferior parietal lobule (IPL) or middle frontal gyrus (MFG). **C.** During unresponsiveness induced by 1.2% sevoflurane, FC between the PCC and both anterior DMN components (mPFC and MFG) and posterior DMN (IPL) is weakened. Average **D.** FC among DMN regions is significantly reduced ($p < 0.05$, unpaired t-test). A: Anterior. P: Posterior. Adapted from [name] et al., 2015[41].

2.1.6 Functional Neuroimaging of Delirium Episodes

Considering logistics and safety, only a single study[56] has investigated resting-state fcMRI in patients with delirium. **These data are not from our group but are reproduced as preliminary data to support the potential role of the DMN in delirium pathogenesis.** Reduction in MRI FC between anterior and posterior

DMN regions during delirium is shown in **Figure 3**. The precuneus region (**Figure 3A**) used in this analysis is a deep posterior DMN region adjacent to the PCC. Regions with significant connectivity to the precuneus are plotted in transverse and sagittal section color t-maps as in (**Figure 2B**). DMN connectivity is recapitulated in t-maps of control patients (**Figure 3B**) with areas of high significantly high positive correlations (yellow and red) to DMN components, including the medial prefrontal cortex (mPFC, arrow). In contrast, significant mPFC-precuneus FC is spatially limited in patients during delirium (**Figure 3C**, arrowhead).

Comparison maps from 13/20 patients following recovery from delirium (**Figure 3D**) demonstrates minimal significant precuneus-mPFC connectivity. Censoring of motion artifact, now recognized by the neuroimaging community as a source of spurious differences in FC[57], also was not performed. **Since fcMRI was not performed prospectively before delirium, it is unclear whether fcMRIDMN connectivity in those who previously experienced delirium was similar to controls (Figure 3B).**

[figure not shown]

Figure 3. Weakening of fMRI functional connectivity between anterior and posterior DMN regions. Adapted from Choi et al., 2012[56]. **A.** Precuneus region used for FC analysis. **B.** FC t-maps from controls show significant DMN FC in the medial prefrontal cortex (mPFC, green arrow, N=22). **C.** Significant FC between the precuneus and the mPFC is substantially limited during delirium (N=20). **D.** Reduction in DMN FC is not restored after recovery from delirium (N=13). A: Anterior. P: Posterior.

2.1.7 Bedside Functional Neuroimaging

Recent work by members of our team ([name], [name]) have allowed the generation of high density diffuse optical tomography systems for assaying task-evoked and resting-state functional connectivity. The imaging system relies on fiberoptic cables implanted in a wearable cap. The fibers are arranged in a grid such that sources and detectors are interspersed along the scalp to allow measurements of near-infrared light (750 nm and 850 nm) in a manner similar to cerebral oximetry. Preprocessing of multiple overlapping measurements of light intensity include source modeling, spectroscopy, and atlas reconstruction to generate oxy- and deoxyhemoglobin maps as a surrogate of neural activity. fcDOT has been recently validated against fcMRI[58, 59], with superficial regions of the DMN accessible by fcDOT[58] (**Figure 4A-B**). A portable clinical system has also been developed[60]. Using this system, fcDOT is currently in use for bedside imaging of RSNs during natural sleep with simultaneous EEG lasting several hours ([name], [name], [name], **Figure 4C-E**). Sleep staging and censoring of motion artifact is performed prior to FC analysis. Maps plotting FC to a left frontal region demonstrate bilateral connectivity during rapid eye movement sleep (REM) that is reduced during slow wave sleep (SWS). As EEG during delirium demonstrates slower frequencies in a similar manner as SWS and other sleep stages, these data lend feasibility toward imaging fluctuations in FC that mirror established electrophysiologic correlates and symptomatology. As shown in **Figure 4G**, the cart and fibers of the portable fcDOT system are not expected to impact clinical care, even in the intensive care unit.

2.1.8 Existing Infrastructure for Tracking Delirium

We are involved in the ENGAGES Trial to assess an association between postoperative delirium and intraoperative EEG suppression (NCT02241655, NIH 1UH2AG050312-01, 4UH3AG050312-02, PI, [name]). The ENGAGES study has enrolled at least 3 cardiac surgical patients per week. Over its first 19 weeks, the incidence rates of delirium are 26% for CABG, 30% for valve, and 71% for combined CABG valve procedures. Cardiothoracic intensive care unit nurses routinely assess for delirium at least once per shift, with routine notation in medical records.

2.2 Objectives

The **rationale** underlying our research agenda is that electrophysiologic and neuroimaging during manifestation and recovery from postoperative delirium may provide markers for future translation into preoperative risk stratification and diagnosis. Our goal is to substantiate commonly used EEG markers of postoperative delirium (Aim 1), utilize bedside optical imaging techniques to investigate DMN connectivity during delirium (Aim 2), assess for functional neuroimaging markers that distinguish patients based on delirium incidence and severity (Aim 3), and investigate the relationship between preoperative DMN FC and postoperative delirium (Aim 4) .

Specific Aim 1: Establish that EEG slowing during postoperative delirium reverses after recovery.

Hypotheses: Relative delta and theta power in frontoparietal EEG are greater during delirium than after resolution. Relative alpha power in frontoparietal EEG is lower during delirium than after recovery.

Specific Aim 2: Determine if DMN connectivity is weaker during delirium than after recovery

Hypothesis: Postoperative DMN FC, measured by fcDOT, is weaker during delirious epochs than after delirium resolution.

Specific Aim 3: Establish whether postoperative DMN FC distinguishes delirious patients from controls.

Hypothesis: Postoperative DMN FC, measured by fMRI and fcDOT, is weaker in those who developed postoperative delirium compared to those who did not experience delirium.

Specific Aim 4: Investigate the relationship between preoperative DMN FC and postoperative delirium.

Hypothesis: Preoperative DMN FC measures will be greater for those who do not experience delirium and will vary inversely with peak postoperative delirium severity.

[figure not shown]

Figure 4. Feasibility of fcDOT imaging of superficial DMN in the perioperative environment. A. The dorsolateral medial frontal gyrus (MFG), an anterior superficial region of the DMN, is accessible to fcDOT. B. Comparison of FC maps fcDOT and fcMRI FC. fcDOT data were acquired from healthy volunteers using a stationary fcDOT system, reproduced from [name] et al., 2014[58]. C, D. Volunteer wearing a clinical system cap currently in use for long recordings (> 8 hours) during fcDOT sleep studies comparing rapid eye movement sleep (REM) and slow-wave sleep (SWS). Sleep staging is accomplished using EEG.

2.4 Design and Participants:

2.4.1 Study Design

This prospective observational study is geared toward longitudinal imaging and electrophysiology study of cardiac surgical patients at Barnes-Jewish Hospital. Patients who are recruited in the delirium arm will serve as their own controls in comparisons of EEG and fcDOT data (**Aims 1 and 2**) to study neural correlates of the delirious state. Secondary analysis are planned to compare these measures between patients who experienced delirium and control patients.

Case-control comparisons of both fMRI and fcDOT DMN FC between patients who did and did not experience delirium (**Aim 3**) will provide information on whether reduced DMN FC may be a correlate of vulnerability to

postoperative delirium, as well as whether preoperative DMN FC is associated with postoperative delirium (**Aim 4**).

2.4.2 Pre-Study Period: None

2.4.3 Subject Screening, Enrollment, and Consent Process:

Sixty-six patients who have had cardiac surgery will be recruited in the Center for Preoperative Assessment and Planning (CPAP), Center for Advanced Medicine (CAM), cardiothoracic intensive care unit (CT-ICU), or step-down floors of Barnes-Jewish Hospital (BJH) in St. Louis. Depending on equipment and research personnel availability, patients may be recruited before or after surgery.

Given that the incidence of postoperative delirium is not predictable for an individual and to spare the cost and resources associated with consenting all cardiac patients, a partial HIPAA waiver will be obtained to allow preliminary eligibility screening of patients based on electronic medical records. Research personnel will screen the surgery schedule for Barnes-Jewish Hospital for procedures fitting the inclusion criteria the following week. Surgeries that meet inclusion criteria will then be screened for all eligibility criteria prior to surgery and being approached. Information regarding eligible patients will be kept in a screening log that will be destroyed once recruitment is complete.

Depending on equipment availability, research personnel may approach eligible patients in CPAP, CAM, CT-ICU, or step-down floors before surgery for consent. Patients consented before surgery will undergo preoperative fMRI, fcDOT, and EEG within one month before surgery, as well as a baseline CAM assessment. If patients are approached preoperatively and there is not enough time for preoperative testing to take place (i.e. patient enrolled day before surgery), patients will complete a baseline CAM assessment before surgery and participate in postoperative testing. Patients not consented before surgery will be approached as early as postoperative day 1 following surgery. To screen for dementia at baseline, we will apply the AD8[61].

Preoperative: For patients consented before surgery, full written informed consent will be obtained directly from the patient. Consent may take place in CPAP, CAM, CT-ICU or step-down floors of BJH. **The participant's previous medical record will be reviewed to ensure they meet all inclusion & exclusion criteria.**

Research personnel may contact possible patients identified by the CPAP or surgery schedule by phone prior to their CPAP appointment. Since many patients will have their CPAP appointment the day before surgery, calling patients to confirm interest will allow enough time to schedule the preoperative MRI scan, which typically takes a minimum of 24 hours. Research personnel will discuss the study using a phone script and, if the patient is interested in the study, will go over the inclusion and exclusion criteria with the patient to ensure eligibility. Research personnel will then meet the patient at Barnes-Jewish Hospital on the day of their CPAP appointment or on a day at the convenience of the patient for written informed consent. Due to the availability of the scanner and the patient, preoperative testing procedures may take place on a different day than the CPAP appointment. Written informed consent will be obtained prior to any study procedures.

Postoperative: For patients consented after surgery, mental status of the patient will be assessed by the study team or by monitoring electronic medical records for signs of altered mental status. Consent will take place in the CT-ICU or step-down floors at Barnes-Jewish Hospital. **Delirious:** Given that the patient will be unlikely to provide full informed consent, and to respect the vulnerability of the study population, a legal authorized representative will be approached for informed written or verbal consent. Lack of dissent/tacit assent will be obtained from the patient prior to any study procedures. The patient will not be enrolled if he or she refuses to participate at this time. **Control:** Consent will be obtained directly from the patient.

For each study participant, modifications including session termination will be pursued on any signs of physical or emotional distress. For patients who experience postoperative delirium, full written informed consent will be obtained after delirium resolution for study participation at subsequent time points if delirium resolution occurs before hospital discharge. Patients may withdraw from the study at any time.

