2.4.4 Inclusion/Exclusion Criteria

Table 1 lists the inclusion and exclusion criteria common to both patient study arms.

Inclusion Criteria	Exclusion Criteria
Age \geq 60	Implanted pacemaker
Surgery requiring cardiopulmonary bypass for Coronary artery bypass grafting (CABG), aortic repair/replacement, septal myectomy, and/or heart valve repair/replacement	Automatic internal cardiac defibrillator
English Speaking	Other implant for which MRI is contraindicated
	Concomitant cerebrovascular procedure or requirement of deep hypothermic circulatory arrest
	Inability to lay flat or still for MRI
	Legal blindness or severe deafness
	Seizure history
	Known focal brain lesion larger than 3 cm

Table 1: Common Inclusion and Exclusion Criteria for Study Enrollment

Delirium Case Arm: Delirious as diagnosed by the Confusion Assessment Method (CAM)/Confusion Assessment Method for the Intensive Care Unit (CAM-ICU) at some point during postoperative day 1-5. The presence of hypoactive delirium will be confirmed after consent has been obtained and prior to measurements.

Postoperative Control Arm: Not delirious as diagnosed by the CAM on postoperative day 1-5.

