Postoperative Sessions 1-3: Approximately 1 hour each. These sessions will occur between postoperative days 1-8. A CAM assessment will be completed to determine delirium outcome prior to other procedures. If patients are intubated at the time of assessments, the Confusion Assessment Method for the Intensive Care Unit (CAM-ICU)[62] will be used. If the patient is sedated (RASS level -4 or -5), delirium will not be assessed. Patients may also be assessed using the CAM-ICU if the patient's current condition cannot tolerate the long-form of the CAM. Research personnel will also assess for pain using the Behavioral Pain Scale (BPS)/Behavioral Pain Scale for Non-Intubated Patients (BPS-NI), depending on the status of the patient, and the Visual Analog Scale (VAS) pain scores. Patients will then be asked to sit upright and still for three 10 minute periods while watching television or moving toes or fingers to maintain wakefulness. EEG and fcDOT data will be acquired. An additional 15 minutes of data will be acquired while patients keep their eyes closed. To maintain wakefulness, patients will be asked to keep moving their toes or fingers. Patients will also listen to an auditory recording for 3 minutes while EEG and fcDOT data is acquired. These data will maximize interpretability by allowing localization of auditory cortex. Pulse oximetry may be used during data acquisition, with supplemental oxygen, if needed.

Session 4-5: Approximately 2 hours. This will occur during the period between disconnection of chest tubes and within 1 month after hospital discharge. A CAM assessment will be completed to determine delirium outcome prior to other procedures. Patients may also be assessed using the CAM-ICU if the patient's current condition cannot tolerate the long-form of the CAM. Research personnel will assess for pain using the Behavioral Pain Scale (BPS)/Behavioral Pain Scale Non-intubated (BPS-NI), depending on the status of the patient, and the Visual Analog Scale (VAS) pain scores. Patients will be asked to sit upright and still for 30 minutes while watching television or moving toes or fingers to maintain wakefulness. EEG and fcDOT data will be acquired. An additional 15 minutes of data will be acquired while patients keep their eyes closed. To maintain wakefulness, patients will be asked to keep moving toes or fingers. Patients will also listen to an auditory recording for 3 minutes while EEG and fcDOT data is acquired for source localization.

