3.3 Recruitment and Informed Consent

Screening and enrollment of subjects will occur according to the protocol-defined inclusion and exclusion criteria. Given that the incidence of postoperative delirium is not predictable for an individual and to spare the cost and resources associated with consenting all cardiac patients, a partial HIPAA waver will be obtained to allow preliminary eligibility screening of patients based on electronic medical records. Research personnel will screen the surgery schedule for Barnes-Jewish Hospital for procedures fitting the inclusion criteria the following week. Surgeries that meet inclusion criteria will then be screened for all eligibility criteria prior to surgery and being approached. Information regarding eligible patients will be kept in a screening log that will be destroyed once recruitment is complete.

Depending on equipment availability, research personnel may approach eligible patients in CPAP, CAM, or step-down floors before surgery for consent. Patients consented before surgery will undergo a preoperative fMRI, fcDOT, and EEG within one month before surgery. Patients not consented before surgery will be approached as early as postoperative day 1 following surgery and extubation. To screen for dementia at baseline, we will apply the AD8[61].

Preoperative: For patients consented before surgery, full written informed consent will be obtained directly from the patient. Consent may take place in CPAP, CAM, ICU, or step-down floors.

Postoperative: For patients consented after surgery, mental status of the patient will be assessed by the study team. Consent will take place in the CT-ICU or step-down floors at Barnes-Jewish Hospital. **Delirious:** Given that the patient will be unlikely to provide full informed consent, and to respect the vulnerability of the study population, a legal authorized representative will be approached for informed written or verbal consent. Lack of dissent/tacit assent will be obtained from the patient prior to any study procedures. The patient will not be enrolled if he or she refuses to participate at this time. **Control:** Consent will be obtained directly from the patient.

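### The consent route after surgery may rest on the chart alone under section 2.4.3 but not under section 3.3, and re-consent is not required when delirium resolves after discharge

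*Combined protocol and SAP*

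**What the plan says.** **Choosing who consents.** For postoperative enrolment, section 2.4.3 (Postoperative paragraph) states "mental status of the patient will be assessed by the study team or by monitoring electronic medical records for signs of altered mental status". Section 3.3 covers the same step and states "For patients consented after surgery, mental status of the patient will be assessed by the study team", with no chart alternative. In both sections the answer sets the route. For a delirious patient, "a legal authorized representative will be approached for informed written or verbal consent", and the patient must also not dissent. For a control, "Consent will be obtained directly from the patient".

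**Order of consent and delirium testing.** Section 2.4.4, in the definition of the delirium case arm, says "The presence of hypoactive delirium will be confirmed after consent has been obtained and prior to measurements". Sections 2.4.5 and 2.4.7.4 put the study CAM at the start of each session, ahead of the other procedures. Neither ties it to the choice of consent route.

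**Re-consent.** For patients who experience delirium, section 2.4.3 says "full written informed consent will be obtained after delirium resolution for study participation at subsequent time points if delirium resolution occurs before hospital discharge". Section 3.3 repeats this, and section 2.8 (Participant Satisfaction) carries the same limit in similar words.

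**Session 4.** Section 2.4.5 says of the session with EEG, fcDOT and a one-hour MRI: "This will occur during the period between disconnection of chest tubes and within 1 month after hospital discharge". Section 2.8 allows the MRI to be done as an outpatient. Sections 2.4.5, 2.4.7.3 and 2.4.7.4 require a CAM on the day of the scan.

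**The concern.** Representative consent is the protocol's stated protection for a vulnerable group. It works only if delirium is recognised before the route is chosen. The background (section 2.1.1) explains why recognition may fail: "Without direct verbal interrogation, clinicians can misdiagnose" the hypoactive subtype, which it calls the predominant one. It adds that symptoms fluctuate, so the timing of an assessment can miss them. A rule that lets the record suffice is weakest for this subtype.

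The second issue comes at the other end of follow-up. Re-consent exists so that a recovered patient can decide on further participation. The rule as written stops at discharge, while study procedures continue after it.

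The recordings at stake belong to the case arm, for which 33 patients are planned: delirium sessions for Aims 1 and 2, and postoperative connectivity measurements for Aim 3. A missing consent step cannot be supplied after the recording has been made.

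**Working it through.** The plan gives no figure for this point, so the check sets the provisions side by side.

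**A. The consent route**

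1. Section 2.4.3 joins study-team assessment and record monitoring with an *or*, so either is enough. Section 3.3 allows the first only. Staff cannot tell from the protocol whether a chart review is sufficient. Neither section names the CAM or a capacity assessment as the basis.
2. What the chart holds depends on the ward. Section 2.1.8 says nurses in the cardiothoracic ICU assess for delirium at least once per shift and record it. Step-down floors, where postoperative consent is also taken, are not covered by that statement.
3. The next check is the CAM at the start of the session, before measurements. It can detect a delirious patient who has self-consented.
4. Three provisions might say what follows:
   - Section 2.7.1 assigns the patient to the delirium arm. That settles the analysis group, not the consent.
   - The re-consent rule covers everyone who experiences delirium, but acts only after resolution, and only in hospital.
   - The representative route in section 2.4.3 is described for patients already judged delirious when approached.
5. None of these covers the interval between the positive CAM and resolution, which is when the delirium recordings for Aims 1 and 2 are made.

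**B. Re-consent**

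| Patient | Own consent obtained or required? |
|---|---|
| Consented before surgery | Yes, in writing, from the patient |
| Enrolled after surgery through a representative, recovers in hospital | Yes, after resolution |
| Enrolled after surgery through a representative, recovers after discharge, session 4 or MRI after discharge | No rule requires it |

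In the third row, the CAM at session 4 or on the scan day would show that the patient has recovered, but a negative result triggers no consent step.

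**C. Size**

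The documents give no sensitivity for chart review, no count of patients routed on the chart alone, and no count of patients still delirious at discharge. For gap A, one can calculate the share of chart-negative patients who are delirious, with assumed prevalence *p*, assumed chart sensitivity *s* and no chart false positives:

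p(1 − s) / [p(1 − s) + (1 − p)]

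- p = 0.10, s = 0.75: 0.025 / 0.925 = 2.7%
- p = 0.10, s = 0.50: 0.050 / 0.950 = 5.3%
- p = 0.30, s = 0.75: 0.075 / 0.775 = 9.7%
- p = 0.30, s = 0.50: 0.150 / 0.850 = 17.6%

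Both inputs are assumptions, and the formula treats the chart as the only basis. It gives no credit to study-team assessment or to the consent conversation. It is an illustration, and the conclusion does not rest on it.

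**The case against.** The strongest reply is that the protocol already has several safeguards:

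- Study-team assessment is named in both sections.
- ICU records contain bedside delirium assessments by nurses.
- Consent is taken from the patient in person, so someone speaks with them.
- A CAM precedes every set of measurements.
- The sentence that places confirmation after consent belongs to the case-arm definition and does not describe how controls consent.
- For representative-consented patients, absence of dissent is needed before study procedures, refusal bars enrolment, and withdrawal is possible at any time.
- The study is described as minimal risk. Consent pages are not part of the text reviewed, so further procedures there cannot be ruled out.

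Most of this stands, and it rules out some stronger readings. A reader might infer that the route *is* chosen on chart signs; the text only permits it, in one of two conflicting sections. A reader might infer that delirious patients end up analysed as controls; section 2.7.1 says otherwise, so the concern is with the consent route and not the arm. A reader might also infer that chart review misses precisely the hypoactive patients; section 2.1.1 says only that misdiagnosis can occur.

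Three things are not answered: the conflict between sections 2.4.3 and 3.3, the missing rule after self-consent followed by a positive CAM, and the discharge limit on re-consent. Absence of dissent and the right to withdraw soften the last of these, but they are not the patient's own consent.

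**Conclusion.** The point holds in this form. The re-consent gap follows directly from the text: a patient enrolled after surgery through a representative, whose delirium clears only after discharge and who attends session 4 or the MRI after discharge, can be recorded and scanned without giving their own consent. The consent-route gap is an inconsistency between two sections plus one missing rule. It does not amount to a chart-based consent policy.

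The number affected is unknown and probably small, since the re-consent gap needs all of those conditions together. Patients who consented before surgery or re-consented in hospital fall outside it.

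It would go too far to conclude that consent already taken is invalid or that data would have to be withdrawn. The documents state neither, and section 2.4.3 says only that delirious patients are unlikely to be able to give full consent, which is not automatic incapacity. No test, sample size or arm assignment changes. Severity is moderate: the matter is participant protection, the gaps can be read from the text, and the correction is cheap.

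**What to change.** 1. **Reconcile section 2.4.3 with section 3.3.** The study team assesses mental status in person before the consent route is chosen, with the medical record as supporting information only.
2. **Add a rule for a positive first-session result.** If the first postoperative session CAM or CAM-ICU is positive in a patient who self-consented after surgery, recording waits until the study team has checked whether that consent stands. If it does not, representative consent and the patient's assent are obtained first. The check allows for a patient who was lucid at consent and became delirious later.
3. **Remove the discharge limit.** In sections 2.4.3, 2.8 and 3.3, delete the closing condition that restricts re-consent to resolution before discharge. Require the patient's own consent at the first session after resolution, including a post-discharge session 4 or MRI, once the CAM already scheduled there has been done. Apply this to any patient who has so far taken part only on representative consent, so that those who have already consented for themselves are not asked again.

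The cost is a short wording amendment for IRB approval. No new instrument or visit is needed. A few sessions may be delayed while consent is checked or a representative is reached, and a few recovered patients may decline session 4.
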